9. RESEARCH DESIGN AND METHODS

This is a randomized, 2-arm (1:1), double blinded clinical trial comparing pain scores at the time of osmotic dilator insertion and at specific points after insertion with a buprenorphine plus 1% lidocaine paracervical block compared to a paracervical block alone in women who have osmotic cervical dilators placed.

Primary Hypothesis:

In patients undergoing osmotic dilator insertion in preparation for dilation and evacuation, the addition of buprenorphine 0.15mg to a 1% lidocaine paracervical block will be associated with lower mean pain scores at time of osmotic dilator insertion compared to women who receive a 1% lidocaine paracervical block alone.

Secondary hypotheses:

In patients undergoing osmotic dilator insertion in preparation for dilation and evacuation, the addition of buprenorphine 0.15mg to a 1% lidocaine paracervical block will be associated with lower mean pain scores 2 hours after osmotic dilator insertion compared to women who receive a 1% lidocaine paracervical block alone.

In order to investigate this hypothesis, the following study design is proposed:

We plan to recruit at two study sites – the University of California, San Diego (UCSD) and Planned Parenthood of the Pacific Southwest (PPPSW). The UCSD study team will be responsible for all study procedures conducted at Planned Parenthood. Members of the UCSD study team will be determining eligibility, consenting patients, administering patient questionnaires, collecting data, and performing data analysis. Planned Parenthood clinicians will be administering the study medication during the procedure and will not be involved in any other research procedures.

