Included in the study are women who present to the UCSD or PPPSW clinics seeking dilation and evacuation for any indication and who will require cervical preparation with osmotic dilators as determined by the evaluating clinician. Patients between 14 weeks 0 days gestation to 23 weeks 6 days gestation at the time of osmotic dilator insertion will be candidates for study inclusion. Participants will be excluded based on a brief questionnaire if they have a known allergy to the study medication or ibuprofen, any chronic pain conditions, have taken any narcotic medications in the last 24 hours, have chronic opiate use or any other drug abuse, request sedation during laminaria insertion, or have a history of chronic liver disease. Stratified randomization will be performed among participants based on vaginal parity (nulliparous and multiparous). Participants will be randomized to one of two study groups allocated one to one: (1) paracervical block with 20mL of 1% buffered lidocaine or (2) paracervical block with 20mL of 1% buffered lidocaine plus 0.15mg of buprenorphine.

During the procedure, the study team member will present the numeric rating scale (NRS) to the participant and ask her to mark her level of pain at each time point during the procedure (paracervical block placement, osmotic dilator insertion, 5 minutes post procedure) and will remain blinded to the study arm. These NRS scores will be recorded into REDCap utilizing an electronic tablet. The participant will be asked

about side effects such as dizziness and nausea during the procedure. The clinician will perform the osmotic dilator insertion in the usual fashion, and the study team member will record the time from speculum insertion to speculum removal.

After the procedure, the clinician will answer a brief questionnaire detailing if there were any adverse events or difficulty related to either the paracervical block or the osmotic dilator insertion. The clinician will also note whether or not cervical dilation was performed prior to osmotic dilator insertion and to what size dilator. They will also indicate their level of training. At 5 minutes after osmotic dilator insertion, the participant will indicate her level of pain and answer questions regarding side effects and satisfaction with pain control during the procedure.

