The table below indicates the time point at which the various assessments will be performed. Assessments will be performed over one to two days: on the day of osmotic dilator insertion and on the day of D&E. If same day dilators are used, the final assessment will be performed immediately prior to D&E. Overall, the process of clinician evaluation, procedural consent, study recruitment, study consent, performance of procedure, and immediate post-procedure questionnaire should take about 30 minutes. The follow up questionnaires and questionnaire prior to D&E will take about 10 minutes. Participants will receive a questionnaire sent via text message link at 1 hour, 2 hours, and 6 hours post-procedure. This questionnaire

assesses the need for oral analgesics for pain as well as participant satisfaction with their pain control at that study point. Participants will take a questionnaire on the morning of D&E asking them to rate their current pain and to recall their maximum pain score over the preceding day and their overall satisfaction with their pain control. The need for follow up will be determined per usual clinician practice and preference.

Randomization:

Block randomization will be performed in alternating blocks of 4 and 6 stratified by vaginal parity (vaginally nulliparous versus vaginally multiparous). The study team member will open the designated sealed sequentially numbered opaque randomization envelope containing computer generated randomization code of the type of paracervical block and hand it to the clinician performing the procedure. A clinician who will not be administering the paracervical block will then open the envelope and prepare the designated paracervical block into two 10 mL syringes. A different clinician blinded to the treatment group will perform the standardized procedure for osmotic dilator insertion using a speculum, 25-gauge spinal needle to inject the paracervical block, Dennison dilators to dilate the cervix if that is the clinician's practice, and insertion of laminaria and/or Dilapan-S. The amount of time it takes to inject the paracervical block will be recorded.

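### The Randomization paragraph names two openers of the allocation envelope and sends it to the operator, who is supposed to be blinded

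*Combined protocol and SAP*

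**What the plan says.** The opening of section 9 sets the design: "This is a randomized, 2-arm (1:1), double blinded clinical trial comparing pain scores".

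The Randomization paragraph of section 9 then gives the operating steps. After a sentence on block sizes and stratification, it continues with three steps:

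1. "The study team member will open the designated sealed sequentially numbered opaque randomization envelope containing computer generated randomization code". The rest of that sentence gives the content of the code and the recipient of the envelope: "of the type of paracervical block and hand it to the clinician performing the procedure".
2. In the following sentence: "A clinician who will not be administering the paracervical block will then open the envelope and prepare the designated paracervical block". Two syringes are made up.
3. In the sentence after that: "A different clinician blinded to the treatment group will perform the standardized procedure for osmotic dilator insertion". The same sentence lists injection of the block among this clinician's tasks.

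Earlier in section 9, in the description of the procedure, "the study team member will present the numeric rating scale (NRS) to the participant", asks her to mark her pain at each time point, "and will remain blinded to the study arm". Once the insertion is complete, "the clinician will answer a brief questionnaire detailing if there were any adverse events or difficulty related to either the paracervical block"; the question covers the dilator insertion as well. The Outcomes list in section 9 adds a survey of the provider performing the procedure, which covers ease of dilator placement and major complications.

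**The concern.** The Randomization paragraph is the only place in the documents that says who handles the envelope, so it is the working instruction on which the blind depends. It gives one envelope two openers and delivers it to the one clinician who must not see its contents. Staff have to disregard part of the instruction to keep the blind.

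Two things are at stake. The first is the operator's own reports, which are secondary data but include adverse events and complications. The second is the blinding of whoever presents the pain scale, if that person is also the one who opens the envelope.

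**Working it through.** There is no statistical figure to reproduce. The check sets the three steps side by side.

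| Step | Who opens | Who holds the envelope afterwards | Must that person be blinded? |
|---|---|---|---|
| 1 | Study team member | Operator | Yes, by step 3 |
| 2 | Non-administering clinician | The same clinician, who prepares the syringes | No |
| 3 | – | – | Operator is blinded and is not the preparer |

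**Could steps 1 and 2 be alternatives?** No. Step 2 is worded as following step 1, so the same envelope is opened twice, and on the second occasion it is no longer sealed.

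**Could the recipient in step 1 be the preparer?** No. The recipient is the clinician performing the procedure. Step 3 gives the procedure, including injection of the block, to a different clinician from the preparer.

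**Could the code hide the arm?** Not on this text. The code is for the type of block, and the preparer makes up the assigned block from it. No separate key and no inner envelope is mentioned.

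**Who is unblinded under step 1?**
- *The operator:* yes. This reaches the post-procedure questionnaire and the provider survey.
- *The person presenting the pain scale:* only if that person opened the envelope. Section 9 uses the same role name for both tasks. Section 12 lists a research coordinator, a research assistant and co-investigators among those who may obtain consent, so the team has several members, and the documents do not say whether one individual does both tasks.
- *The participant:* nothing in the step tells her the arm. She marks the primary pain score herself.

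**Reach.** The Power Calculation in section 9 takes 104 women and adds 10%: 104 × 1.10 = 114.4, stated as 114. With one envelope per participant (an assumption), the step is carried out up to 114 times. This counts how often the instruction is used. It does not measure bias.

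**The case against.** The strongest reply is that nobody would act on step 1 alone. Staff must also follow steps 2 and 3, which with the double-blind statement make the intended scheme plain. The verb in step 1 may be a slip for obtaining the envelope. The aims in section 6 also do not depend on operator ratings: pain and satisfaction are rated by the participant, she is asked about side effects, analgesic use comes from her questionnaires, and the 2-hour score is collected through a text link.

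Most of this stands. It limits the finding to an error in an operational step. It does not remove the error, because correcting the verb would still leave the envelope going to the operator. There are two mistakes in the sentence, opener and recipient, and both need correcting.

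A reader might infer more than the text supports:

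- *That the trial is planned without effective blinding.* Steps 2 and 3 provide a separate preparer and a blinded operator.
- *That the primary comparison is biased.* An operator who knew the arm might behave differently, but any effect on a score that the participant marks would be indirect. The documents give no size for it, nor a standard deviation from which to work one out.
- *That the person presenting the pain scale is certainly unblinded, or that a recruiter who opens envelopes could anticipate later assignments from the stated blocks of 4 and 6.* Each requires one individual to hold both roles, which the documents neither state nor exclude.

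**Conclusion.** The contradiction is real and should be fixed. The paragraph names two openers and the wrong recipient, and nothing else in the documents settles the matter.

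If step 1 is followed as written, one effect is certain: the operator is unblinded, and so are the operator's reports of difficulty, adverse events, ease of placement and major complications. The effect on the person presenting the pain scale is conditional on that person being the opener. No effect on the primary pain score is shown, and none is estimated here.

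This rests on two readings: that the envelope's code identifies the arm to anyone who sees it, and that the clinician performing the procedure in step 1 is the operator of step 3. The text supports both. It does not show that any participant was, or would be, treated unblinded.

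**What to change.** Replace step 1 with wording such as:

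> The study team member takes the next numbered opaque envelope for the participant's parity stratum and passes it, unopened, to the preparing clinician, who will not administer the block.

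Keep step 2, so that only the preparing clinician opens the envelope. Add one sentence stating that the allocation is not disclosed to the operator, the participant or the person presenting the pain scale.

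Two further matters are for the sponsor:

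- Keeping the preparing clinician out of outcome collection is an optional safeguard. It is an added rule, and its cost depends on staffing at each site.
- The preparer's role at the Planned Parenthood site needs reconciling with the design description in section 9. That text limits Planned Parenthood clinicians to giving the study medication and excludes them from other research procedures. Opening envelopes and preparing blinded syringes may fall outside that limit, so the plan should say who does this there.

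The core cost is a wording change to an existing step, using roles already planned. Sample size and analysis do not change.

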6. SPECIFIC AIMS

Primary aim:

To compare the mean pain score at the time of osmotic dilator insertion among women randomized to a 1% lidocaine and buprenorphine paracervical block compared to a 1% lidocaine paracervical block alone.

We hypothesize that in patients undergoing osmotic dilator insertion in preparation for dilation and evacuation, the addition of buprenorphine 0.15mg to a 1% lidocaine paracervical block will be associated with lower mean pain scores at time of osmotic dilator insertion compared to women who receive a 1% lidocaine paracervical block alone.

Secondary aims:

1. To compare the mean pain score 2 hours after osmotic dilator insertion among women randomized to a lidocaine and buprenorphine paracervical block compared to a lidocaine paracervical block alone.
2. To assess overall narcotic and ibuprofen use after osmotic dilator placement and before dilation and evacuation procedure.
3. To assess opioid related side effects.
4. To determine patient satisfaction with pain control during and after osmotic dilator insertion.

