The primary outcome of the study is pain as measured on the NRS at the time of osmotic dilator insertion. Studies have varied in the time point at which pain is measured during the procedure, as some assessed pain with dilator insertion and others have recorded it 5 minutes after dilator insertion⁸⁻¹¹. Research studies addressing pain *during* osmotic dilator insertion have used the VAS, while studies looking at pain *after* dilator insertion have used the numeric rating scale (NRS)⁸⁻¹¹. We plan to capture pain using the NRS (an 11-point scale from 0-10) as we are evaluating pain at multiple different timepoints, both during and after dilator insertion.

Our secondary outcome is pain at 2 hours post dilator insertion. Given that buprenorphine can extend the length of analgesic effect by 2-3 times, we anticipate that the prolonged anesthetic effect should last anywhere from 2-6 hours using 1% lidocaine and provide pain relief as the dilators are expanding. Patients will be receiving text messages with links to questionnaires at three different time points (1 hour, 2 hours, and 6 hours post-insertion) in order to assess their level of pain, analgesic use, as well as any other symptoms. These text messages will be time stamped depending on time of dilator insertion and will be sent out at the intervals

	Before procedure	Paracervical block	Osmotic dilator placement (0 minutes)	5 minutes post dilator placement	1 hour post dilator placement	2 hours post dilator placement	6 hours post dilator placement	Prior to D&E
Baseline survey	x							
Pain scale	x	x	x	x	x	x	x	x
Side effect assessment			x	x	x	x	x	x
Clinician survey				x			x	
Assessment of oral analgesic medications needed					x	x	x	x
Participant satisfaction with pain control				x	x	x	x	x

we specify in the text messaging software.

Schedule of Assessments

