Intervention: A paracervical block with 20mL of 1% buffered lidocaine plus 0.15mg of buprenorphine will be injected prior to osmotic dilator insertion. A paracervical block with 20mL of 1% buffered lidocaine will be used in the control group. The patient will not be charged for the study drug. All drug costs will be covered by the study (this is also stated in the consent form).

Outcomes:

- 1) Sociodemographic and clinical data:** age, race, ethnicity, level of education, marital status, height, weight, obstetric history, history of cervical procedures (e.g. LEEP procedure or Conization), chronic baseline pain
- 2) Primary outcome:** Level of pain as rated on an 11-point (0-10) numeric rating scale during osmotic dilator insertion.
- 3) Secondary outcomes:**
 - a. Pain (Numeric Rating Scale):
 - i. Baseline (before procedure)
 - ii. Paracervical block placement
 - iii. 5 minutes post procedure
 - iv. 1 hour post procedure
 - v. 2 hours post procedure
 - vi. 6 hours post-procedure
 - b. Satisfaction
 - i. Likert scale questions
 1. How satisfied are you with the amount of pain control that you had during the procedure?
 2. If you had to have these dilators placed for a procedure in the future, would you choose to have the same pain medication that you received today?
 - c. Adverse events – side effects at time of paracervical block placement and after procedure
 - d. Survey of provider (resident, fellow, attending, advance practice clinician) performing procedure
 - i. Number of dilators placed

- ii. Ease of osmotic dilator placement
- iii. If patient will return for second set of dilators
- iv. Major complications
- v. Type of clinician (resident, attending, advance practice clinician)

No specimens will be collected for research purposes. All research data will be collected on electronic tablets and de-identified via REDCap.

Power Calculation:

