It is suggested that a 2-point reduction in pain on the numeric rating scale (NRS) is clinically meaningful.²⁴⁻²⁷ No existing study parallels the outcomes of our proposed research (pain at time of osmotic dilator insertion using the numeric rating scale). One previous study used the Visual Analog Scale (a 0-100mm linear scale) to compare pain at the time of osmotic dilator insertion between a 1% lidocaine paracervical block and vaginal lidocaine gel.⁸ The visual analog scale and the numeric rating scale have modest correlation.⁴² The median pain score during osmotic dilator insertion in the 1% lidocaine paracervical block group was 61 (which correlates to 6 on the numeric rating scale) with a range from 0-100.

In order to detect a 2-point difference on the NRS at the time of osmotic dilator insertion with 80% power and a two-sided alpha of 0.05, we will need a total of 52 patients in each study arm (26 per arm). We plan to stratify the groups by vaginal parity (nulliparous versus multiparous) as vaginal parity may affect pain at the time of osmotic dilator insertion. In order to stratify by vaginal parity, we will need a total of 104 women (52 in each strata) to see a difference between strata per group. We plan to enroll an additional 10% to account for protocol deviation and participant dropout for a total of 114 participants. With a one to one randomization allocation, approximately half will be randomized to receive a paracervical block with buprenorphine and 1% lidocaine and half will receive a paracervical block with 1% lidocaine alone. Additionally, randomization will be stratified by vaginal parity (vaginally nulliparous versus vaginally multiparous).

Data Analysis

The baseline participant survey, NRS scores, side effects, and post-procedure participant and provider surveys will be performed by the study coordinator using REDCap loaded on to an electronic tablet. This data will be transferred to a spreadsheet in SPSS. Bivariate comparisons will be analyzed using chi squared test or Fisher’s Exact test for categorical variables and t-test or Mann-Whitney for continuous variables depending on the distribution of the data as appropriate. The primary outcomes will be evaluated per intent-to-treat analysis.

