14. POTENTIAL RISKS

- 1) Loss of confidentiality
- 2) Pain with paracervical block injection or insertion of osmotic dilators
- 3) Side effects of the study medication include feeling sleepy, vertigo, dizziness, headache, fatigue, itching, sweating, nausea, constipation, vomiting, temporary elevation of liver enzymes
- 4) Rare side effects of the study medication include swelling, bruising or redness at the injection site; low blood pressure; constricted pupils; fainting; or slow breathing.
- 5) Unknown risks
- 6) Risk of randomization: one assigned study group might prove to be less effective or have more side effects than the other study group

We will be purchasing intramuscular naloxone in the rare event of respiratory depression from systemic absorption of the buprenorphine. This is an extremely rare anticipated side effect as the partial mu-agonist properties of this drug typically causes a ceiling effect and prevents respiratory depression. However, we will have this medication on hand in clinic in case of this extremely rare event.

Each clinic site is equipped with basic emergency equipment in the rare event that a medical emergency should happen during the study procedures. In the rare event of serious side effects (such as slowed breathing), naloxone would rapidly reverse all side effects. Given the low dose of buprenorphine being administered, only one dose of naloxone would be necessary to reverse the effects of the medication.

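### Side effects at the block are a listed outcome, but the schedule starts the assessment at dilator placement and no pre-block symptom check is described, which dilutes the side-effect comparison

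*Combined protocol and SAP*

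**What the plan says.** All references are to the combined protocol and SAP.

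- Section 6, secondary aim 3: "To assess opioid related side effects".
- Section 9, Outcomes, item 3c (adverse events): "side effects at time of paracervical block placement and after procedure".
- Section 9, narrative of the procedure: the participant is asked "about side effects such as dizziness and nausea during the procedure". The same paragraph gives the pain-score time points during the procedure as "paracervical block placement, osmotic dilator insertion, 5 minutes post procedure", so the block falls inside that period.
- Section 9, Schedule of Assessments: the row "Side effect assessment" is marked at dilator placement, 5 minutes, 1, 2 and 6 hours, and before the D&E. Its pre-procedure and block columns are empty. The pain row is marked in all eight columns.
- Section 9, Outcomes, item 1: the baseline list ends with "history of cervical procedures (e.g. LEEP procedure or Conization), chronic baseline pain". It names no nausea, dizziness, sleepiness or similar symptom. A baseline survey is scheduled before the procedure, but its items are not shown.
- Section 14: "Side effects of the study medication include feeling sleepy, vertigo, dizziness, headache, fatigue, itching, sweating, nausea, constipation, vomiting".
- Section 9, Data Analysis: "Bivariate comparisons will be analyzed using chi squared test or Fisher’s Exact test for categorical variables". No baseline adjustment and no rule for new or worsened symptoms is given.

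**The concern.** There are two linked gaps. First, the outcome list and the narrative both place a side-effect question at or around the block, and the schedule does not. Staff working from the schedule would collect nothing at one of the two times that outcome 3c names.

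Second, several expected effects (sleepiness, dizziness, headache, fatigue, nausea) are non-specific, and a pregnant woman may have them before any injection. The plan measures pain before the procedure, but describes no matching check for these symptoms. If every later report counts, women who were already symptomatic are events in both arms, and the contrast between arms shrinks. Secondary aim 3 is the trial's tolerability comparison for a drug that the protocol says has not been studied in a paracervical block, so a loss of sensitivity there works against finding a real excess. Symptom status before the block cannot be reliably recovered later.

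**Working it through.** **Side by side.** For side effects at the block, outcome 3c says yes, the narrative says yes by implication (no exact time point or checklist), and the schedule says no. For side effects before the block, none of the three describes an assessment.

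**Inputs.** The plan gives no power figure for side effects, so there is none to reproduce. From Section 9, Power Calculation: 104 women before the dropout allowance, allocated 1:1, so 104 / 2 = 52 per arm; two-sided alpha 0.05. Assumed, because the documents give no rates: prior prevalence b of 10% to 40%, and new-onset rates q0 = 10% (control) and q1 = 30% (buprenorphine).

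**Three ways to count.**

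1. Any report: p = b + (1 − b)q in each arm, n = 52.
2. New onset among all randomised women: p = (1 − b)q, n = 52.
3. New onset among women free of the symptom before the block: p = q, n = 52(1 − b).

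The risk difference is (1 − b)(q1 − q0) under counts 1 and 2, and q1 − q0 under count 3. Count 2 therefore does not restore the risk difference. It restores the risk ratio to q1/q0 = 3.0 and lowers the variance, and the power gain comes from the lower variance.

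**Power.** Φ[(d − 1.96·se0)/se1], where d is the risk difference, se0 = √(2p̄(1 − p̄)/n) and se1 = √([p0(1 − p0) + p1(1 − p1)]/n).

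Worked case, b = 30%:

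- Any report: 0.37 v 0.51, d = 0.14, p̄ = 0.44, se0 = 0.0973, se1 = 0.0964. Power = Φ[(0.14 − 0.1908)/0.0964] = Φ(−0.53) = 0.30.
- New onset, all randomised: 0.07 v 0.21, d = 0.14, p̄ = 0.14, se0 = 0.0681, se1 = 0.0667. Power = Φ[(0.14 − 0.1334)/0.0667] = Φ(0.10) = 0.54.

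| b | Any report: rates | RR | Power, any report | Power, new onset, all randomised | Power, new onset, symptom-free |
|---|---|---|---|---|---|
| 0 | 10% v 30% | 3.00 | 0.73 | 0.73 | 0.73 |
| 10% | 19% v 37% | 1.95 | 0.53 | 0.67 | 0.68 |
| 20% | 28% v 44% | 1.57 | 0.40 | 0.61 | 0.63 |
| 30% | 37% v 51% | 1.38 | 0.30 | 0.54 | 0.57 |
| 40% | 46% v 58% | 1.26 | 0.23 | 0.47 | 0.51 |

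**Sensitivity to the assumed rates** (any report against new onset among all randomised):

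- b = 5%, 10% v 30%: 0.62 against 0.70.
- b = 10%, 10% v 50%: 0.98 against 0.99.
- b = 10%, 20% v 30%: 0.16 against 0.19.

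**No drug effect.** With a 10% new-onset rate in both arms and any report counted, the type I error of Fisher's exact test at 52 per arm is 1.9% at b = 0, 3.3% at b = 30% and 3.8% at b = 50%. Prior symptoms do not produce a false signal.

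**The case against.** A reader might infer that symptoms present before the injection would be mistaken for drug effects, biasing the comparison. The documents do not support that. The trial is randomised, double blind and has a lidocaine-only arm, so prior symptoms balance on average and the type I error stays below 5%. What remains is a higher raw rate in each arm and lower power.

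A reader might also infer that nobody asks about side effects at the block. The narrative has them asked about during the procedure, a period that includes the block, and the clinician's questionnaire afterwards covers adverse events related to the block. The schedule also has an assessment at dilator placement, the next step of the same visit. At the block this is a conflict between text and schedule, not a proven absence. None of these supplies the woman's status before the injection.

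Three further objections stand in part. The rates are all assumed, and the gain is close to nil when the drug effect is very large or too small to detect either way. The model also takes every prior symptom to persist and be reported later; transient symptoms would dilute less. The survey and side-effect forms are not shown, so a baseline symptom item or a question worded for new symptoms cannot be ruled out. Finally, side effects are a secondary aim with no hypothesis or power claim, so lost power breaks no promise in the plan.

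**Conclusion.** The point holds as a cheap improvement. The schedule disagrees with outcome 3c and with the narrative on side effects at the block, and no section describes a pre-block symptom check or a new-or-worse rule. If any later report counts, prior prevalence b multiplies the risk difference by (1 − b) and pulls the risk ratio toward 1. That direction follows from the counting rule, provided prior symptoms persist and are reported.

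The size is illustrative only. At 52 per arm, with new onset of 10% v 30% and b from 10% to 40%, power is 0.53 to 0.23 when any report counts, against 0.67 to 0.47 for new onset among all randomised women (0.68 to 0.51 among symptom-free women). These figures count new onset only; symptoms that worsen are not modelled. The analysis of the primary pain outcome is unaffected.

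**What to change.** 1. Reconcile the Section 9 narrative, the schedule and outcome 3c by marking the side-effect assessment in the paracervical block column, with a stated checklist.
2. Add the same symptom items to the REDCap survey already completed before the procedure, and mark that column too.
3. In Data Analysis, define the side-effect outcome as a symptom that is new, or worse than before the block, and compare it among all randomised women with the planned chi-squared or Fisher test. Report the pre-block prevalence by arm.

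Grading worse needs a simple severity scale on each item at both times. The cost is a few items on an existing form and about a minute of participant time. Sample size and the primary analysis do not change.

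### The base sample size is given as both 52 and 26 per arm with no SD to decide between them, and the power claimed by parity has no quota or test behind it

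*Combined protocol and SAP*

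**What the plan says.** Section 9, Power Calculation, sets the target at a 2-point difference on the 0-10 NRS during dilator insertion, with 80% power and two-sided alpha 0.05. The base requirement is "we will need a total of 52 patients in each study arm (26 per arm").

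The next step concerns parity: "we will need a total of 104 women (52 in each strata) to see a difference between strata per group". Then: "We plan to enroll an additional 10% to account for protocol deviation and participant dropout for a total of 114 participants".

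The only information on spread comes from an earlier trial that used the VAS. Its median in the lidocaine block group "was 61 (which correlates to 6 on the numeric rating scale) with a range from 0-100". The plan adds that "No existing study parallels the outcomes of our proposed research". No SD is given.

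Elsewhere in section 9, under Randomization: "Block randomization will be performed in alternating blocks of 4 and 6 stratified by vaginal parity". Under Data Analysis: "Bivariate comparisons will be analyzed using chi squared test" or Fisher's exact test for categorical variables, with a t-test or Mann-Whitney test for continuous ones. The primary aim in section 6 is "To compare the mean pain score at the time of osmotic dilator insertion among women randomized" to the two blocks. Neither the aims in section 6 nor the hypotheses in section 9 mention parity.

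**The concern.** There are two faults in the same paragraph.

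First, the base size is stated twice with values that differ by a factor of two. The SD would settle which was meant, and it is absent, so no reader can reproduce the calculation.

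Second, the step to 104 is presented as something that stratifying by parity requires, and as giving power for a comparison involving parity. Stratified randomization balances the arms within each stratum. It does not require a doubled sample, and it does not fix how many women fall in each stratum. A by-parity power claim needs a stratum size that the plan secures and an analysis that the plan names, and neither is present. Left as it is, the sentence could be cited later to support by-parity conclusions that the trial was not designed to give.

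**Working it through.** **Inputs from the plan.** Difference 2 NRS points, two-sided alpha 0.05, power 80%, 1:1 allocation, 104 evaluable, 114 enrolled. The SD is not stated, so every SD below is an assumption and a range is shown.

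**Step 1: what each reading implies.** For two means, n per arm = 2 × SD² × (1.96 + 0.84)² / 2². Solving for the SD gives SD = 2 × √(n/2) / 2.80.
- n = 26: 2 × √13 / 2.80 = 2.57; the exact noncentral-t calculation gives 2.52.
- n = 52: 2 × √26 / 2.80 = 3.64; noncentral t gives 3.61.

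The remaining figures use the noncentral t. The n per arm needed for 80% power is:

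| Assumed SD | 2.5 | 3.0 | 3.5 | 3.6 | 4.0 |
|---|---|---|---|---|---|
| n per arm | 26 | 37 | 50 | 52 | 64 |

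Either stated figure can therefore be correct for some plausible SD. If the SD were 3.6, 26 per arm would have 50% power.

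**Step 2: do the later totals decide it?**
- 26 per arm: 26 × 2 arms = 52; 52 × 2 strata = 104.
- 52 per arm: 52 × 2 arms = 104.
- Inflation: 104 × 1.10 = 114.4, stated as 114. This step is not in dispute.

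Both readings reach 104.

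**Step 3: the primary comparison at the planned size.** Power for 2 points, arms pooled over parity:

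| Assumed SD | 2.5 | 3.0 | 3.5 | 4.0 |
|---|---|---|---|---|
| 52 per arm (104) | 98% | 92% | 82% | 71% |
| 57 per arm (114) | 99% | 94% | 86% | 75% |

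At 52 per arm, power stays at or above 80% up to an SD of about 3.6.

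**Step 4: the by-parity claim.** The phrase about strata can be read in two ways.

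*Arm effect within one stratum.* With 52 women split 26:26, power for 2 points is 81% at SD 2.5, 65% at 3.0 and 50% at 3.6. With 104 women at SD 2.5, an uneven parity mix lowers power in the smaller stratum (splits assumed):
- 50:50, 26 per arm: 81%.
- 40:60, 104 × 0.4 / 2 = 20.8 per arm: 71%.
- 30:70, 104 × 0.3 / 2 = 15.6 per arm: 58%.

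*Difference in arm effect between strata.* With 26 per cell, SE = SD × √(4/26). At SD 2.5 this is 2.5 × 0.392 = 0.98, and 2 / 0.98 = 2.04 on 100 df, which gives about 52% power for a 2-point interaction.

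If 52 per arm was the base requirement (SD about 3.6), 80% power within each stratum would need 52 × 2 × 2 = 208 women, not 104.

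**The case against.** The strongest reply is that the contradiction is a slip for 52 in total, 26 per arm. The words giving a total of 52, the figure in parentheses and the step from 52 to 104 through two strata all fit 26 per arm. If the base were already 52 per arm, stratifying would add nothing to the total. A rough rule of SD = range/4 applied to the 0-100 VAS range gives 25 mm, or 2.5 NRS points, and hence 26 per arm. On that reading a stratum of 52 split evenly has 81% power for the arm effect, which meets the plan's own target. Recruitment is the same either way.

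Most of this is fair. 26 per arm is the likelier meaning, and the recruitment target is unaffected. But range/4 is not an input the plan gives, so the SD remains unstated even if the slip is granted. The 81% also depends on that SD and on a near-even parity split that nothing in the plan secures.

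Two further points are fair. The power figures here are for a t-test, whereas the plan also allows Mann-Whitney. With the usual normal-theory relative efficiency of 0.955, the SD at which 52 per arm gives 80% power moves only from 3.61 to 3.52. The sponsor could also keep a by-parity aim instead of withdrawing it, but would then have to supply the stratum targets and the analysis.

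**Conclusion.** The concern holds and should be fixed. As written, the base size is either 26 or 52 per arm, corresponding to an SD of about 2.5 or 3.6, and the plan gives no SD to decide between them. The by-parity power claim is not secured on either reading: it needs both an SD near 2.5 and a near-even split on the likelier one, and it falls to about 50% on the other. Taken as an interaction, it has about 52% power even at SD 2.5 with equal cells.

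This is not a finding that the trial is too small. The pooled primary comparison is adequately powered at 104 unless the SD exceeds about 3.6; its power is simply not stated. All power figures rest on assumed SDs and a two-sample t-test.

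**What to change.** No change in sample size. Three changes to section 9:

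1. **Power Calculation, base size.** Give one figure: 52 patients in total (26 per arm) or, if that was meant, 104 in total (52 per arm). State the assumed SD in NRS points and its source.
2. **Power Calculation, justification of 104.** Tie the target to the primary comparison, for example: *The target is 104 evaluable women (52 per arm), 114 enrolled. Because no earlier study measured this outcome on the NRS, the SD is uncertain. For the primary comparison of arms across both parity strata (two-sample t-test, two-sided alpha 0.05), 52 per arm keeps at least 80% power for a 2-point difference up to an SD of about 3.6: 98% at SD 2.5, 92% at 3.0, 82% at 3.5; it falls to 71% at SD 4.0.* This also explains why 104 is kept if the base figure is confirmed as 52 in total.
3. **Parity.** Replace the sentence on 52 per stratum with: *Randomization is stratified by vaginal parity for balance.* Add to Data Analysis: *Effects by parity are descriptive, reported with a treatment-by-parity estimate and 95% CI; the trial is not powered for them.*

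The cost is wording, one sourced SD and a restated power figure. The sponsor gives up the by-parity power claim.
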